#### Minimizing Risks:

- **Risks of Very Low Carbohydrate Diet:** In order to minimize the symptoms associated with transitioning to a low carbohydrate diet abruptly, participants will be encouraged to stay hydrated to help them acclimate and avoid unwanted symptoms.
- **Hypoglycemia/Hyperglycemia:** Participants will be contacted frequently during the course of the study. Blood draws will be done frequently during the HRU/CSRJU/Masonicare admission to minimize hypoglycemia and hyperglycemia. Intravenous glucose will be available in case hypoglycemia occurs. All infusates containing insulin are prepared under a filtration cabinet (Laminated HLDA filter) by qualified personnel using sterile disposable materials.
- Participants will be encouraged to monitor closely for signs of glycemic deterioration and will be able to contact our diabetes staff at any time if concerns arise.
- At the end of each visit, the participant will receive guidance for glucose monitoring, food intake, and insulin dosing as needed.
- During the study, insulin doses will be adjusted regularly (2-3 times per week as needed) to prevent hypoglycemia. Participants will use a real-time CGM that will provide alerts at the time of hypoglycemia and allow for early detection of hypoglycemia as well. Participants will be trained on treatment of hypoglycemia and to contact the study team immediately in any case of severe hypoglycemia.
- If any participant has 2 episodes of severe hypoglycemia, they will be transitioned to a regular diet after the 2nd episode of severe hypoglycemia.
- **Stable isotopes:** Isotopes will be carefully monitored, administered and will be prepared in the investigational pharmacy to ensure proper technique. As noted in

previous protocols using this stable isotope, the pyrogenicity and sterility of the isotopes are documented by Cambridge Isotopes before they are shipped to YNHH IDS. Methods to Ensure Compound Sterility and Pyrogenicity: All stable isotopes are purchased from Cambridge Isotopes (Boston, MA) and are sent to us sterile and pyrogen-free as specified in the certification form of analysis that is attached to each order. In addition, all infusates containing the isotope that will be used in the study are prepared by the Yale Investigational Drug Service (IDS) by using specific filters (0.22 $\mu$ ). Furthermore, we also use microfilters at the end of each syringe as another safety precaution. All stable isotopes are stored by the Yale IDS and are sent to the YCCI the morning of the study.

- Risk of Indirect Calorimetry: Potential feelings related to wearing the “hood” will be discussed with participants ahead of time, if participants become uncomfortable while wearing the hood it will be removed.
- Risk of indwelling catheter: IV insertion will be performed by trained research nurses on the HRU/CSRU/Masonicare. Trained nurses will use aseptic technique to insert the IV catheters. We will minimize the risk of pain by offering an option of topical anesthetic to the patient prior to IV insertion. Participants will be advised to contact the study team immediately if they become aware of a late adverse effect.
- Anemia: Samples will be obtained with the minimum necessary blood volume. The point of care YSI glucose determinations require only 0.3ml of blood. We will ensure that blood volume obtained does not exceed a maximum of 5 mL/kg in pediatric participants and 250 mL in adult participants. We limited the lower limit of weight to 43 kg so as not to exceed blood draw volumes.
- Risk of loss of confidentiality: All study staff are HIPPA certified. Participant names and study records will be kept confidential. The IRB may inspect study records at any given time. All efforts will be made to maintain the participants' privacy. Each participant will be assigned a study ID code and data will be linked by this study ID rather than by names, initials, social security numbers, or other personal identifiers. Paper documents will be stored in locked areas accessible only to authorized staff. All electronic data files will be protected by passwords limiting access to the files only to those with a legitimate responsibility for data entry or management. This ensures that, in the unlikely event that any primary data sources from this study are lost or misplaced, it will not be possible to identify the study participant. Copies of informed consent/assent forms and families' contact information will be stored separately from the other study data, which will not contain names or other identifying information. Identifiable study information will be maintained for 10 years after the research is complete. After that time, it will be destroyed or de-identified. The principal investigator will keep a link that identifies subjects to coded information, but this link will be kept secure and available only to the PI or selected members of the research team.
- Risk of CGM: Risks of glucose sensor insertion will be minimized because participants will be instructed to cleanse skin aseptically prior to insertion. Participants will receive training on sensor use if they have not used the sensor previously.
- Risk of study questionnaires: Study staff and social work will be contacted to support families as needed.

### 3.2.2 Potential Benefits:

- Participants may experience improved glycemic control by participating in the study.
- Participants may learn more about how the macronutrient content of food can affect blood sugar levels.
- Long-term benefits of this research are a generalizable understanding of the changes of insulin resistance and counterregulatory hormone responses to

hypoglycemia relate to dietary changes for youth with T1D, which will help to inform future treatment strategies.

## 4 Study Objectives

### 4.1 Hypotheses

Aim 1: We hypothesize that, compared to a standard carbohydrate diet, adolescents with T1D on a very low carbohydrate diet will spend more time in the target glucose range, will have a more robust response to hypoglycemia, and will lessen hypoglycemia awareness.

Aim 2: We hypothesize that counterregulatory hormone response to hypoglycemia (glucagon production) will be amplified in a very low carbohydrate diet when compared to standard carbohydrate diet. This will occur because of lower insulin doses on the very low carbohydrate diet that will translate to lower glycogen stores, and amplify the counterregulatory hormone response to hypoglycemia.

Aim 3: We hypothesize that hypoglycemia symptoms will be blunted on a very low carbohydrate when compared to a standard carbohydrate diet.

### 4.2 Primary Objective

The primary objective of this study is to determine whether youth with type 1 diabetes will improve glycemic control (increase time in the target glucose range of 70-180 mg/dL) following a very low carbohydrate diet when compared to a standard carbohydrate diet.

### 4.3 Secondary Objectives (if applicable)

The secondary objectives of this study are to compare the metabolic responses to hypoglycemia when adolescents are on a very low carbohydrate diet to a standard carbohydrate diet. We will also compare glucose and glycerol metabolism using stable isotope infusions between the two diets. We will use a 2-step hyperinsulinemic euglycemic-hypoglycemic clamp. Nonradioactive stable isotope infusions of glucose and glycerol will be given during the clamp to measure changes in glucose and glycerol metabolism (hepatic glucose production and adipose tissue lipolysis).

### 4.4 Exploratory Objectives (if applicable)

We will compare symptoms of hypoglycemia during hyperinsulinemic hypoglycemic clamp in adolescents with T1D following a very low carbohydrate versus standard carbohydrate diet. Participants will report symptoms of hypoglycemia during euglycemia and hypoglycemia portions of each clamp to determine if hypoglycemia awareness is affected by each type of diet. Further, interviews will be conducted to collect descriptive qualitative data about participants' and parents' experiences following a very low carbohydrate diet.

## 5 Study Design

**5.1 General Design Description:** Currently, there are no specific dietary recommendations for adolescents with T1D. To fill this gap in knowledge, we will study a very low carbohydrate diet that limits carbohydrate intake to 15% of total daily calories. We hypothesize that, compared to a standard carbohydrate diet, adolescents with T1D on a very low carbohydrate diet will spend more time in the target glucose range, will have a more robust response to hypoglycemia, and will lessen hypoglycemia awareness. To test these, we will conduct a randomized crossover study to compare the metabolic and neurological responses to hypoglycemia in adolescents after following each isocaloric diet.

**5.1.1 Study Date Range and Duration:** 4 years

**5.1.2 Number of Study Sites:** The enrollment visit will take place at the Pediatric Diabetes Research Center at [name]. The clamp procedures will take place at the CSRU, HRU, and Masonicare.

### 5.2 Outcome Variables

#### 5.2.1 Primary Outcome Variables

**Aim 1:** The primary efficacy outcome will be the time spent in the target range of 70-180 mg/dL during the second week on each diet. Secondary safety outcomes will include the time spent in the hypoglycemic (less than 54 mg/dL, less than 70 mg/dL) and hyperglycemic (greater than 180 mg/dL, greater than 250 mg/dL) ranges. We will also measure the average sensor glucose values, standard deviation, and coefficient of variation during the second week on each diet period. We will compare average and range of fasting beta-hydroxybutyrate levels during each diet period. Number of episodes of diabetic ketoacidosis and severe hypoglycemic events during each period (baseline, diet periods, and washout period) will also be reported.

**Aim 2:** The primary safety outcome will be the mean levels of glucagon produced in response to hypoglycemia after each diet will be measured using a 2-step hyperinsulinemic euglycemic-hypoglycemic clamp. These will be measured after 15, 30, 45, and 60 minutes of euglycemia and hypoglycemia. Secondary safety outcomes will include mean levels of other counterregulatory hormones (cortisol, epinephrine, norepinephrine), and beta-hydroxybutyrate that are produced in response to hypoglycemia during the clamp will be compared after each 2-week diet period. Fasting levels of glucagon, free fatty acids, beta-hydroxybutyrate and IGF-1 (measure of growth hormone secretion), prior to the clamp will be compared after each diet period. Secondary outcome measures will include hepatic glucose production and adipose tissue lipolysis, which will be measured using stable isotope infusions during the euglycemic and hypoglycemic portions of the clamp. We will compare differences in hepatic glucose production during each clamp between a standard and very low carbohydrate diet. Additionally, deuterated water will be utilized to differentially evaluate the contribution of gluconeogenesis and glycogenolysis to endogenous glucose production.

**Aim 3:** The primary safety outcome will be hypoglycemia awareness symptoms that occur after 20-30 minutes of euglycemia and hypoglycemia during each clamp using a validated Edinburgh Hypoglycemia Symptom questionnaire. Scores during euglycemia will be compared to scores during hypoglycemia for each clamp. Scores during hypoglycemia after each diet period will also be compared. To describe how participants feel about and react to following a very low carbohydrate diet, interviews will be conducted over

zoom (HIPAA compliant). Data will be coded and emerging patterns will be combined into descriptive themes.

### **5.3 Study Population**

Participants will be youth ages 12 and <25 with a diagnosis of type 1 diabetes for at least 1 year and have an A1c level < 10%. Participants will be recruited from the Yale Pediatric Diabetes Center and Yale Diabetes Center. Participants will also be recruited from ClinicalTrials.gov and social media (Facebook, Twitter, Instagram). The Yale Pediatric Diabetes Center Clinics, which sees over 1000 pediatric patients each year. Of those, 425 patients are between the ages of 12 and 18 with type 1 diabetes each year. It is estimated that 255 (60%) in this age group have an A1c level of < 10% and will be eligible for the study. Based on this information, 85 potential participants are seen each month in our clinics. We anticipate being able to recruit at 10% (8-9 participants) of these patients each month, which is more than enough to complete the study. All participants will undergo pre-screening of their electronic medical record to evaluate study eligibility by review of age and previous laboratory tests. Flyers will also be distributed in the clinics. Participants who meet eligibility criteria may also be contacted by MyChart. Patients who have already completed the study will be contacted about follow up interviews that will be voice-recorded over zoom.

**5.4 Number of Participants:** 20 total participants will be needed to complete the study.

**5.4.1 Eligibility Criteria/Vulnerable Populations:** The principal investigator ([name]) will determine eligibility and inclusion/exclusion criteria.

In order to be eligible to participate in this study, an individual must meet all of the following criteria:

1. Provision of signed and dated informed consent form by the adult (if person is at least 18 years old) or parent and assent form if the participant is <18 years old.
2. Stated willingness to comply with all study procedures and availability for the duration of the study
3. Male, female, transgender, nonbinary are all eligible
4. Ages 12 to <25 years, inclusive, of all races/ethnicities
5. Diagnosis of type 1 diabetes for at least 1 year
6. Hemoglobin A1c level < 10% within the past 2 months
7. Insulin pump use for at least 2 months.
8. Ability to perform daily blood ketone checks, wear a continuous glucose monitor, willing to wear an activity monitor, willing to adhere to the study diets and keep a diet journal.
9. For females of reproductive potential: use of highly effective contraception for at least 1 month prior to screening and agreement to use such a method during study participation and for an additional 4 weeks after the end of the dietary intervention.
10. For males of reproductive potential: use of condoms or other methods to ensure effective contraception with partner

An individual who meets any of the following criteria will be excluded from participation in this study:

1. Current use of glucose-lowering agents other than insulin
2. Unstable psychiatric disorders, including eating disorders (DSM-V criteria).
3. Weight loss medications within the last 6 months
4. Pregnancy or lactation, or planning pregnancy within the next 6 months
5. BMI < 19 kg/m^2 for individuals 18 years of age or older

6. BMI < 5%ile for individuals under 18 years
7. Weight less than 49 kg or 108 pounds (due to blood draw)
8. Other medical conditions that may interfere with glucose metabolism and insulin sensitivity (as determined by the investigator).

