**Aim 3:**

Primary Safety Outcome: We will measure hypoglycemia awareness symptoms after 20-30 minutes of euglycemia and hypoglycemia during each clamp using a validated Edinburgh Hypoglycemia Symptom questionnaire. Scores during euglycemia will be compared to scores during hypoglycemia for each clamp. Scores during hypoglycemia after each diet period will also be compared.

Primary Efficacy Outcome: To describe how participants feel about and react to following a very low carbohydrate diet, interviews will be conducted over zoom (HIPAA compliant). Data will be coded and emerging patterns will be combined into descriptive themes.

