- **Risks of ketosis:** Risks of the very low carbohydrate diet include the development of elevated ketone levels. These will be monitored frequently in the outpatient setting and all supplies will be provided to participants. Participants will also be educated on warning signs of DKA and will be instructed to call the study team for any elevated ketone levels  $> 1$  mmol/L or if they have symptoms of ketosis (nausea, vomiting, headache). If a participant develops DKA, they will be withdrawn from the study. Hyperglycemic events will be classified as diabetic ketoacidosis (DKA) if all of the following are present:
  - Symptoms of polyuria, polydipsia, nausea, or vomiting;
  - Serum ketone level  $> 1.5$  mmol/L or large/moderate urine ketones;
  - Serum bicarbonate  $< 15$  or venous pH  $< 7.24$  or arterial pH  $< 7.3$ ;
  - Treatment provided in a healthcare facility;
- **Risk of loss of confidentiality:** As in any study, there is the potential for loss of confidentiality. Female subjects of childbearing potential will require urine pregnancy testing prior to enrollment in the protocol, and results of this testing have potential to result in loss of confidentiality.
- **Risk of glycemic deterioration:** It is possible that changing dietary requirements or insulin doses may result in glycemic deterioration. Likewise, adolescents may have glycemic deterioration due to non-compliance. During the study, dose adjustments will be made according to standard of care to prevent hypoglycemia and hyperglycemia.
- **Risk of CGM:** Participants have the option of using FDA approved CGM as part of clinical care in our clinics. There is a low risk of developing a local skin infection at the site of the sensor needle placement. Itchiness, redness, mild bleeding, and or bruising may occur at the insertion site. Subjects may develop localized reactions to adhesive used to secure the sensor.
- **Risk of study questionnaires:** Participants may experience some distress when discussing factors important to diabetes, diabetes management, and psychosocial stressors

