### 6.1 Treatment

#### 6.1.1 Identity of Investigational Product – N/A

#### 6.1.2 Dosage, Administration, Schedule

Visit 1 will consist of informed consent and enrollment. The study will begin with a 1 to 3 -week baseline period for insulin optimization. At visit 2, participants will be randomized for either the very low carbohydrate diet or standard carbohydrate diet that they will follow for 2 weeks. At visit 2 (virtual/telephone/in person), participants will be instructed on how to keep diet journal and report relative amounts of food during the 24-hour recall phone calls. After 2 weeks on the first diet, participants will come to the HRU/CSRU/Masonicare for Visit 3, the hyperinsulinemic euglycemic-hypoglycemic clamp. Following this visit, the participants will have a 1-3 week washout period. At Visit 4 (virtual/telephone/in person), the next diet will be reviewed. They will follow that diet for 2 weeks and then return to the HRU/CSRU/Masonicare for Visit 5 and the second hyperinsulinemic euglycemic-hypoglycemic clamp. After this visit, the study will be complete.

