#### 6.2.4 Pharmacokinetics (if applicable) – N/A

#### 6.2.5 Biomarkers (if applicable) – N/A

### 6.3 Study Procedures

6.3.1 **Study Schedule:** See figure 1. The study will consist of 5 visits: The enrollment visit, randomization, and 2 visits for clamp procedures following each diet and a virtual/telephone follow up visit.

Enrollment Visit 1	Screening and Consent. Discuss research procedures. Meet with a registered dietitian or trained research staff to discuss diet and education on keeping a diet record. Review of insulin pump and CGM data.
Randomization Visit 2 (Virtual/Telephone or in person)	Randomization will occur, as will discussion of subsequent diet (and how to obtain meals), study requirements, and next steps. Review of insulin pump and CGM data.
Clamp Visit 3	Hyperinsulinemic-euglycemic 2-step clamp followed by hypoglycemic clamp. Study questionnaires. Review insulin pump and CGM data. Discussion of washout period and next steps. Review of insulin pump and CGM data
Visit 4 (Virtual/Telephone or in person)	Discussion of subsequent diet (and how to obtain meals), study requirements, and next steps. Review of insulin pump and CGM data.
Clamp Visit 5	Hyperinsulinemic-euglycemic 2 step clamp followed by hypoglycemic clamp. Study questionnaires. Review of insulin pump and CGM data. Discussion of potential need for insulin dose changes and follow up.
Visit 6	Interviews will be conducted over the telephone or over zoom.

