### 6.3.6 End of Study and Follow-up

- Participants will be instructed to contact study staff and make them aware of any adverse events that occur during the study (severe hypoglycemia, diabetic ketoacidosis, etc). Information about adverse events will also be asked at each study follow up visit.
- Upon completion of the clamp procedures, participants will be instructed to monitor their glucose levels carefully and contact clinic staff if they note that

insulin adjustments are needed. Follow up appointments with a diabetes care provider will be recommended within 2 weeks of the end of the study. Their primary diabetes provider will also be contacted and made aware that they have completed the study.

- If participants withdraw from the study early, participants will be instructed to monitor their glucose levels carefully and contact clinic staff if they note that insulin adjustments are needed. Follow up appointments with a diabetes care provider will be recommended within 2 weeks of ending the study. Their primary diabetes provider will also be contacted and made aware that they have withdrawn from the study.
- Diabetes providers will be made aware of any adverse events that take place during the study or information that is considered medically necessary for their overall health. Participants will be made aware of any information that may be shared with their diabetes provider. There is no plan to share results with the primary diabetes providers unless something pertinent to their diabetes management occurs during the study.

**6.3.7 Removal of subjects:** Participants may be withdrawn if they are unable to follow the dietary requirements and study procedures, including keeping a diet journal, testing ketone levels, and wearing a CGM at least 75% of the time.

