### 6.4.2 Sample Size Considerations

For all aims, we base our sample size on the unadjusted comparison of paired means, which is a conservative approach. Therefore, given that our statistical analyses will be based on adjusted models and models that specifically take into account within-person correlation in outcomes of interest, we should be sufficiently powered to answer our research questions.

Aim 1: The goal time in range in adolescents with T1D 60% +/- 10% of their time in the target range of 70-180 mg/dL but based on our preliminary work in this population we expect that the mean percent of time in range is around 50-55%. With 16 eligible subjects, we will have 80% power at the two-sided alpha of 0.05 to detect a minimum increase in the expected mean by 7.5% (from 50-55% on standard carbohydrate diet to 57.5-62.5% on low carbohydrate diet - an increase of 1.5 hours per day - an effect size of  $7.5\% \div 10\% = 0.75$ ), using a paired-sample t-test. If we assume 20% attrition, we will need 20 individuals for the study.

Aim 2: Using data from a previously published study, where changes in glucagon levels during 2-step euglycemic-hypoglycemic clamp in youth with T1D were assessed over a period of 1 year(15), we anticipate that with 16 subjects (n=20 with 20% attrition, see aim 1) we will have 80% power at the two-sided alpha of 0.05 to detect a between-diet change in mean glucagon levels of at least 9.5 pg/mL (standard deviation=12.5 pg/mL, effect size of  $9.5 \text{ pg/mL} / 12.5 \text{ pg/mL} = 0.75$ ), using a paired t-test. We will also report the incremental rise and area under the curve (AUC) as well as mean and peak glucagon levels.

Aim 3: Using estimates of variability (standard deviations [sd]=5 during euglycemia and sd=10 during hypoglycemia) from a previous study, with 16 subjects (20 subjects with 20% attrition) we will have 80% power at the two-sided alpha of 0.05 to detect an effect size in the range of 0.75-1.0, using a paired t-test, meaning that when on low carbohydrate diet, subject

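### As written, participants who stop the very low carbohydrate diet early have no route into the Visit 6 interviews, so the themes could be tilted towards those who managed the diet

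*Combined protocol and SAP*

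**What the plan says.** **Purpose.** In the synopsis (Aim 3): "To describe how participants feel about and react to following a very low carbohydrate diet, interviews will be conducted over zoom". Section 5.2.1 and the table in section 6.2.1 repeat this. The synopsis and the 6.2.1 table label it the primary efficacy outcome of Aim 3. Section 4.4 lists the same interviews among the exploratory objectives.

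**Who is approached.** Section 5.3, at the end of the recruitment paragraph: "Patients who have already completed the study will be contacted about follow up interviews that will be voice-recorded over zoom". No other group is named anywhere.

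**When.** The visit table in section 6.3.1 lists Visit 6 after Clamp Visit 5: "Interviews will be conducted over the telephone or over zoom". Section 6.1.2 says of Visit 5: "After this visit, the study will be complete".

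**Who may leave early.** Section 6.3.7: "Participants may be withdrawn if they are unable to follow the dietary requirements and study procedures". Section 3.2.1 adds: "If a participant develops DKA, they will be withdrawn from the study".

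**What happens to them.** The early-withdrawal item in section 6.3.6 covers glucose self-monitoring, a recommended diabetes appointment and notice to the primary diabetes provider. It mentions no interview.

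**How many.** Section 6.4.2: "If we assume 20% attrition, we will need 20 individuals for the study".

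**The concern.** Selection into the interview is close to the thing being described. A participant who cannot keep to the diet may be withdrawn, and once withdrawn has no written route to the interview about that diet. Those people are among the best informed about what makes it hard to follow. A view that only they hold cannot appear in the transcripts, and the coding and consensus procedures in section 6.4.2 cannot recover it, because they work on the interviews that exist.

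What is at stake is the trial's account of acceptability. Section 2.1.1 already states that both carbohydrate levels can be kept up long term in practice. Interviews drawn from people who finished both diets and both clamps are poorly placed to test that statement.

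**Working it through.** **1. The plan's own figure.** Section 6.4.2 gives 16 evaluable participants, a paired t-test, effect size 0.75, two-sided alpha 0.05 and 80% power.
- Noncentrality = 0.75 × √16 = 3.0, with 15 degrees of freedom. Exact power from the noncentral t is 80.1%, which reproduces the plan.
- Inflation for attrition: 16 / (1 − 0.20) = 20, also reproduced.
- Expected non-completers: 20 − 16 = 4.

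**2. The passages side by side.** Section 5.3 directs the invitation to people who have finished. Sections 6.1.2 and 6.3.1 put the end of the study at Visit 5 and the interview after it. Section 6.3.6 gives those who withdraw a list of follow-up steps without an interview. The Visit 6 text in section 6.3.5 speaks simply of participants and their parents; it neither limits interviews to completers nor adds a route for anyone else. The interview analysis text in section 6.4.2 does not mention non-completers. Staff following these sections would have no instruction to invite a withdrawn participant.

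**3. Who is affected.** This depends on diet sequence and time of leaving. Open-ended diet questions are asked at Visits 3 and 5 (section 6.3.5), so they reach only those who attend a clamp visit.

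| Sequence | Leaves during | Started very low carbohydrate diet? | Open-ended questions answered after it? |
|---|---|---|---|
| Very low first | first diet | yes | no |
| Very low first | washout or second diet | yes | yes, at Visit 3 |
| Standard first | first diet or washout | no | not applicable |
| Standard first | second diet | yes | no |

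The first and fourth rows are the real gap. The second is partly covered. The third has no experience of the diet to report.

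**4. Size.** Let *k* be the number of early leavers who had started the very low carbohydrate diet. The documents give neither reasons nor timing for the 20% attrition, so *k* runs from 0 to 4.

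Illustration, resting on assumptions that are not in the documents: 4 of 16 completers hold an adverse view (4/16 = 25% of interviews), and all *k* early leavers hold it. The share among everyone who started the diet is (4 + *k*) / (16 + *k*).

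| *k* | Share among starters | Share in interviews |
|---|---|---|
| 0 | 4/16 = 25% | 25% |
| 1 | 5/17 = 29% | 25% |
| 2 | 6/18 = 33% | 25% |
| 3 | 7/19 = 37% | 25% |
| 4 | 8/20 = 40% | 25% |

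If nothing is assumed about the early leavers' views, only bounds remain. A favourable theme voiced by 12 of 16 completers (75%) could, at *k* = 4, be held by 12/20 = 60% to 16/20 = 80% of starters. Arithmetic alone does not fix the direction. The expectation of a favourable tilt comes from the reasons for which sections 3.2.1 and 6.3.7 allow or require withdrawal.

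**The case against.** **The plan never says that only completers are eligible.** The sentence in section 5.3 may have been written to permit re-contact of people who had already finished, and the Visit 6 text is unrestricted. This stands. A reader might infer a deliberate exclusion, and the documents do not support that. What they show is one named group and no route for any other.

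**The component is small and descriptive.** Section 4.4 calls it exploratory, and in the synopsis Aim 3 falls under the secondary and exploratory heading. The primary objective is CGM time in range. This stands too. A reader might infer that the selection carries directly into the dietary recommendations mentioned in section 3.2, but that section speaks of the study as a whole and does not tie recommendations to interview themes.

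**Completing is not the same as tolerating.** Withdrawal for non-adherence is permissive and also covers diet journals, ketone testing and CGM wear. Someone who struggled for two weeks but attended both clamps would be interviewed. So selection is related to tolerance, not identical with it.

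**Other data exist.** Diet symptoms are screened at least weekly, participants are called three times a week during diet periods, and Visits 3 and 5 include diet questions and the treatment satisfaction questionnaire. A reader might infer that barriers to the diet would go unrecorded, and that is too strong. But the calls are about symptoms, food intake, ketones and glucose, not about the experience of the diet, and the visit questions miss anyone who leaves during it.

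**Themes are not prevalences.** The planned analysis is qualitative description. An adverse theme voiced by even a few completers would still be reported, so percentage contrasts say little about what the report would contain. The loss that remains is of themes, or reasons for stopping, held only by those who left.

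**Conclusion.** The point holds in a limited form. Followed as written, the plan would probably leave out of the Aim 3 interviews the people who stop because they cannot follow the very low carbohydrate diet or who are withdrawn after diabetic ketoacidosis. The themes could then lean towards those who managed it.

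At the planned attrition, 0 to 4 of 20 participants are affected. This assumes that attrition means not finishing the study and that the invitation follows section 5.3 literally. A reader might take the 25% against 40% row as the expected bias. It is the extreme case: it needs all four leavers to have started the diet and all four to share a view held by a quarter of completers, and the documents support neither.

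Time in range, the clamp outcomes, symptom scores, sample size and power are unaffected. The conflicting labels, primary efficacy in the synopsis and section 6.2.1 but exploratory in section 4.4, mean that the weight to be given to the interviews also needs stating. This is a worthwhile, inexpensive improvement to a descriptive component and no threat to the main conclusions.

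**What to change.** - In section 5.3, and for consistency in the visit table of section 6.3.1 and the Visit 6 text of section 6.3.5, define the interview population as every participant who started the very low carbohydrate diet, including those who stop early.
- In section 6.3.6, add an optional Visit 6 invitation to the early-withdrawal procedure.
- In the interview analysis text of section 6.4.2, commit to reporting the numbers interviewed and not interviewed, with reasons, and to showing themes by completion status.
- Use one label for the interview outcome throughout.

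**Cost.** A short amendment and up to about four more calls of 20 to 30 minutes with the existing script, that is 4 × 20 = 80 to 4 × 30 = 120 minutes of interview time. At the $20 per interview in section 7.1, payments come to at most 4 × $20 = $80. Some withdrawn participants will decline, so the gap will shrink without closing; reporting how many declined lets readers judge what is left. No diet, clamp procedure or clinical rule changes.
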